Nephrology clinic at Brenner Children's Hospital. We will obtain parental consent and subject assent. Inclusion criteria include a diagnosis confirmed with three separate blood pressure measurements $\geq 95\text{th}$ percentile for age, sex, and height. Exclusion criteria include secondary causes such as renovascular hypertension and renal disease. The clinic sees approximately 20 new hypertension patients a month, and we anticipate enrolling 100 patients within the one-year study period. The target population is diverse (approximately 40% black, 40% white, and 20% Hispanic), predominantly male (60%), and 50% obese. Each subject will undergo a thorough evaluation per the standard of care. After baseline study assessment, subjects will be started on an antihypertensive medication per the standard of care by an independent clinician not involved in the study. Subjects will be seen in the clinic every three months per standard of care to obtain labs, monitor their blood pressure, and adjust their medication (see **Figure 1** below). Subjects will be evaluated at 12 months with repeat measurements of the outcomes.

Control Arm 1 – Ten healthy normotensive subjects between the ages of 5 and 17 years will be recruited from a general pediatrics clinic (Cornerstone Pediatrics, part of the Wake Forest Baptist Health system) to obtain samples for measurements of the following outcomes for comparison with the hypertensive participants over the same age range: left ventricular hypertrophy on echocardiograms, urine albumin, uric acid in the blood, FGF23 in the blood, and klotho in the blood and urine, as well as the predictors angiotensin II and angiotensin-(1-7) measured in the blood and urine.

Control Arm 2 – Fifty normotensive subjects with obesity between the ages of 5 and 17 years will be recruited from the Brenner FIT program or the Gastroenterology clinic under the direction of my collaborator [name], who is an associate professor of Pediatric Gastroenterology and the Director of Brenner FIT. Eligible patients will be approached about the study by their physician. Control Arm 2 subjects will undergo measurement of the following outcomes: fatty liver disease on ultrasound, liver function testing (AST, ALT), and uric acid in the blood, all of which are obtained as standard of care. They will also undergo collection of angiotensin II and angiotensin –(1-7) in the blood and urine at the same time as clinical samples are obtained.

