Summary statistics will include frequency distributions, mean with standard deviation, and median with interquartile range. Natural logarithmic transformation will improve continuous variable distributional characteristics as indicated. Chi-square and Fisher's exact tests, t-test, and Wilcoxon Rank-Sum test will evaluate between-group comparisons. Pearson or Spearman correlation coefficients will assess for continuous variable correlations. Bivariate analyses will identify potential confounders of the relationships between the predictors and the outcomes.

We will use general linear and logistic regression models to evaluate the relationships between the predictors and outcome measures. *A priori* covariates include sex and race given their relationships with the RAS and the outcomes. We will investigate potential effect modifiers by employing interaction terms and stratifying analyses. A potential confounder will be included in the multivariate models if i) there is an association between the predictor and outcome at $p < 0.2$, or ii) there is a $> 10\%$ change in the regression coefficient for the predictor-outcome relationship. Covariates will be retained in the final model if $p < 0.05$. A two-sided alpha of 0.05 will be considered statistically significant. We will use Enterprise Guide, Version 7.11 of the SAS System for Windows (SAS Institute Inc., Cary, NC) for all analyses.

Sample Size and Power

With 100 subjects we will have $> 90\%$ power to detect a correlation as low as 0.4 between Ang II and Ang-(1-7) and blood pressure. Based on previous data, we estimate the prevalence of left ventricular hypertrophy is 40-60% before and 10-20% after treatment. We estimate the plasma ratio of Ang II to Ang-(1-7) is at least 7.7 (standard deviation 8.4). Therefore, we will have $> 90\%$ power to detect an odds ratio of 1.15 or higher both at baseline and at one year. The prevalence of albuminuria is 20-60%; therefore the effect size and power we can achieve with 100 subjects will be similar to that achieved for left ventricular hypertrophy.

References

1. The Fourth Report on the diagnosis, evaluation, and treatment of high blood pressure in children and adolescents. *Pediatrics* 2004; 114(Supplement 2):555-576

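### The one-year LVH model has 10–20 expected events for at least four slopes; Firth's penalised likelihood would remove most of a moderate inflation of the odds ratio and keep every estimate finite

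*Protocol*

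**What the plan says.** Under Outcomes, left ventricular hypertrophy (LVH) at baseline and after 12 months is a primary outcome, defined as a binary variable.

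The Statistical Plan states: "We will use general linear and logistic regression models to evaluate the relationships between the predictors and outcome measures". Two adjustment variables are fixed in advance: "covariates include sex and race given their relationships with the RAS and the outcomes". Further terms are open-ended: "A potential confounder will be included in the multivariate models if" one of two conditions is met, namely a screening p below 0.2 or a change of more than 10% in the predictor's coefficient. Covariates stay in the final model if p<0.05. Interaction terms and stratified analyses are also foreseen. No limit on model size and no penalised or exact fit is named.

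Under Study Design, "we anticipate enrolling 100 patients within the one-year study period", with a race mix of about 40/40/20 (black, white, Hispanic) and 60% boys. Under Sample Size and Power, "we estimate the prevalence of left ventricular hypertrophy is 40-60% before and 10-20% after treatment", and with a mean Ang II:Ang-(1-7) ratio of at least 7.7 (SD 8.4) the protocol claims more than 90% "power to detect an odds ratio of 1.15 or higher both at baseline and at one year". On significance: "A two-sided alpha of 0.05 will be considered statistically significant".

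**The concern.** One modelling recipe serves two very different amounts of information. At baseline, 40–60% prevalence puts at least 40 children in the smaller outcome class, so 40/4 = 10 or more per slope with four slopes. At one year there are 10–20 events for the same four slopes.

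With so few events, maximum-likelihood logistic regression has two known weaknesses. A non-zero log odds ratio is biased away from zero. And a covariate category with no events, or only events, has no finite estimate (separation). At stake are the size of a primary estimate and, at the low end of the prevalence range, a model that returns an infinite covariate coefficient.

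**Working it through.** **Inputs from the protocol.** n = 100; one-year LVH prevalence 10–20%; ratio SD 8.4; detectable odds ratio 1.15; two-sided alpha 0.05; sex 60/40; race 40/40/20.

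**Assumptions.** All 100 children have a 12-month echocardiogram (no loss rate is given). The odds ratio of 1.15 is per unit of the ratio (the protocol does not state the unit). The number of screened confounders is unknown, so zero and three were tried.

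**1. The plan's own figure.** For one continuous predictor without covariates, power = Φ(√(n·p·(1−p))·ln(OR)·SD − 1.96). Here ln(1.15) × 8.4 = 1.174, an odds ratio of e^1.174 = 3.23 per SD.

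- p = 0.10: √9 × 1.174 − 1.96 = 1.56, power 94.1%.
- p = 0.15: √12.75 × 1.174 − 1.96 = 2.23, power 98.7%.
- p = 0.20: √16 × 1.174 − 1.96 = 2.74, power 99.7%.

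The stated power above 90% reproduces. Simulated unadjusted power at 10% prevalence is 86% with a normal ratio and 94% with a lognormal one. If 1.15 were per SD, power at p = 0.10 would be only 6%, so the per-unit reading is the one the protocol must intend.

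**2. Events per slope.** The ratio (1), sex (1) and race in three groups (2) make four slopes. Three further covariates would make seven.

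| One-year prevalence | Events | Per slope, 4 slopes | Per slope, 7 slopes |
|---|---|---|---|
| 10% | 10 | 2.5 | 1.4 |
| 15% | 15 | 3.75 | 2.1 |
| 20% | 20 | 5 | 2.9 |

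**3. Chance of an empty race cell.** With 20 Hispanic children and LVH unrelated to race, the chance of no events among them is (1−p)^20: 0.90^20 = 12.2%, 0.85^20 = 3.9%, 0.80^20 = 1.2%.

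**4. Simulation.** Data sets of 100 children were drawn with the ratio at mean 7.7 and SD 8.4 (normal or lognormal), a true odds ratio of 1.15 per unit, the protocol's sex and race mix, and covariates unrelated to LVH. Maximum likelihood and Firth's penalised likelihood were compared.

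- *Full model, maximum likelihood.* The ratio's log odds ratio is too large by a median of about 7–15% over the 10–20% prevalence range. On the protocol's scale, 1.15^1.07 = 1.16 and 1.15^1.15 = 1.17. Per SD, e^(1.174×1.07) = 3.51 and e^(1.174×1.15) = 3.86, against 3.23. With three assumed further null covariates, one set of runs reached 23% at 10% prevalence.
- *After elimination at p<0.05 of all covariates, sex and race included.* Median bias is about 2–7%, and no final model was separated.
- *True odds ratio of 1.* No meaningful bias.
- *Separation in the full model.* About 17–21% at 10% prevalence, 6% at 15% and 2% at 20%. The ratio itself was affected in at most 1.6% of runs with 100 children. With 80 evaluable children (an assumed 20% loss) and seven slopes, separation was 30% at 10% prevalence and 4% at 20%.
- *Firth's fit on the same data.* Median bias lay between −9% and +2%, and estimates stayed finite.
- *Root mean square error of the log odds ratio per SD at 10% prevalence, full model.* About 0.43–0.51 for Firth against 0.59–1.15 for maximum likelihood. After p<0.05 elimination, over the whole prevalence range, it was 0.36–0.47 against 0.40–0.57.
- *Inference under maximum likelihood.* In full-model runs, Wald coverage was 95–97% and type I error 4–6%.

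**The case against.** The strongest reply has four parts.

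*The choice of estimator belongs in a SAP.* The protocol says logistic regression, not maximum likelihood, and Firth's method is a way to fit that same model. The SAP is not at hand and may already specify it. This stands as a limit on the point: the protocol contradicts nothing here. But it fixes model family, covariates, entry and retention thresholds and software, and applies them alike to both time points. A logistic model named without qualification will normally be fitted by maximum likelihood.

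*The retention rule shrinks the model.* This stands in part. If the rule reaches sex and race, most of the inflation goes and the final model is not separated. The protocol calls those two covariates a priori and does not say whether the rule applies to them. The rule also works badly under separation: a separated covariate has a Wald z near 0.001, so it is dropped because its estimate diverged and not because it is unrelated to LVH. The 10%-change entry rule is unstable too. At 10% prevalence a pure-noise binary covariate moved the ratio's coefficient by more than 10% in 14% of data sets, against 6% at 20% prevalence.

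*Separation is a low-end problem.* This stands. At 15–20% prevalence it is uncommon, and it mostly affects a covariate such as the smallest race group, which does not by itself invalidate the ratio's odds ratio.

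*Inference is not harmed.* This stands. At 10% prevalence the bias of 0.09–0.21 on the log scale is under half a standard error (0.46–0.51).

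**Conclusion.** The point holds as a moderate weakness of estimation at one year. With 2.5–5 events per slope, a true effect of the planned size would be overstated by a median of about 7–15% on the log scale in the full model, or 2–7% if elimination also covers sex and race. Separation is a real risk near 10% prevalence and a small one at 20%.

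A reader might infer more: that the one-year odds ratio will be reported too large whatever the truth, that separation is frequent across the expected range, or that the LVH conclusion is unsafe. The documents do not support these readings. The bias needs a true association. The high separation rate belongs to the bottom of the protocol's own prevalence range. Coverage and power are essentially unchanged.

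The sizes rest on an odds ratio of 1.15 per unit, complete follow-up, three race groups, covariates with no effect of their own, and an assumed number of screened confounders. Marked loss to follow-up would make separation more common.

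**What to change.** Add one sentence to the Statistical Plan, for example:

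*Logistic models for LVH at 12 months, and for any other binary outcome with fewer than about 10 events per model coefficient, will be fitted by Firth's penalised likelihood with profile-likelihood confidence intervals.*

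The second clause would also reach albuminuria at the low end of its stated prevalence (20% of 100 is 20 events, or 20/4 = 5 per slope). It would help to say in the same place whether the p<0.05 retention rule applies to sex and race, since the size of the bias depends on it.

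The cost is one sentence and one option in the SAS software already planned. The downside is slight shrinkage of the estimate. Sample size, data collection and the stated power claim need no change.

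### The p<0.05 retention rule can remove a covariate admitted for changing the angiotensin coefficient by more than 10%, and entry criterion (i) does not test the candidate

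*Protocol*

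**What the plan says.** The rule is in the protocol's Statistical Plan, second paragraph. The models are introduced with "We will use general linear and logistic regression models to evaluate the relationships between the predictors and outcome measures". Sex and race are fixed in advance: the a priori "covariates include sex and race given their relationships with the RAS and the outcomes". Every other candidate goes through two steps.

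- **Entry.** Criterion (i) reads "A potential confounder will be included in the multivariate models if i) there is an association between the predictor and outcome at", the threshold being 0.2. Alternatively, under criterion (ii), a candidate enters on a shift of more than 10%, described as a "change in the regression coefficient for the predictor-outcome relationship".
- **Retention.** "Covariates will be retained in the final model if" p < 0.05.

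The retention sentence makes no exception for covariates that entered under (ii), nor for sex and race. Nothing elsewhere in the protocol qualifies it. The Laboratory Assessment section uses the word predictors for angiotensin II and angiotensin-(1-7), so in criterion (i) it means the exposure and not the candidate covariate.

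**The concern.** The two steps measure different things. Criterion (ii) asks how far a covariate moves the exposure coefficient, which is the question that matters for confounding. The retention step asks whether the covariate's own coefficient is significant, which at n = 100 depends largely on power. A covariate can pass the first and fail the second. The final model then omits a variable that the plan's own criterion flagged.

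This is an observational study, so regression adjustment is its main protection against confounding. The adjusted analyses of Aims 1 and 3 are affected, as is any adjusted model under Aim 2, whose hypothesis is worded as a correlation. Both the linear models (blood pressure) and the logistic models (left ventricular hypertrophy, albuminuria) are reached. At stake are residual bias and a two-sided 0.05 level that may not hold.

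Two lesser points arise in the same paragraph. Criterion (i) does not mention the candidate, so for a given predictor-outcome pair it admits every candidate or none. Because it is joined to (ii) by "or", it fails to screen but keeps no confounder out, so on its own it is a wording error. The text also leaves open whether sex and race are exempt from retention. Calling them a priori suggests that they are, and no harm is counted here for them.

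**Working it through.** **Planning figures, for context.** These reproduce and are not disputed.

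- Correlation 0.4, n = 100: power = Φ(atanh(0.4)·√97 − 1.96) = Φ(2.21) = 98.7%, against the stated > 90%.
- Odds ratio 1.15 per unit, SD 8.4: log odds ratio per SD = ln(1.15) × 8.4 = 1.174, an odds ratio of 3.23 per SD. Power = Φ(√(100·p(1−p)) × 1.174 − 1.96), which is 94.1% at 10% prevalence and 99.7% at 20%.

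**One case by hand.** Take standardised variables, a true exposure effect of 0.4 (the planning value), and an assumed confounder with coefficient 0.15 and correlation 0.5 with the exposure.

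- Shift from omitting it: 0.5 × 0.15 = 0.075.
- Relative change: 0.075 / (0.4 + 0.075) = 15.8%, so it passes the 10% criterion.
- Residual variance: 1 − (0.16 + 0.0225 + 2 × 0.4 × 0.15 × 0.5) = 0.7575.
- Standard error of its coefficient: √(0.7575 / (97 × 0.75)) = 0.102.
- t = 0.15 / 0.102 = 1.47, p about 0.14, so it fails retention.

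In expectation, then, this confounder enters and is removed again.

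**Simulation inputs.** n = 100 comes from the protocol. The rest is assumed: one confounder, a normal predictor, and the confounder strengths in the table. Three strategies are compared.

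- *Plan's rule:* enter if the predictor-outcome p < 0.2 or the change exceeds 10%; keep only if the covariate's p < 0.05.
- *Fix:* enter if the candidate has p < 0.2 with both predictor and outcome, or the change exceeds 10%; then keep.
- *Forced adjustment:* the confounder is always in the model.

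There were 20,000 runs per linear setting and 10,000 per logistic setting.

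**False-positive rates with no true effect**

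| Model and assumed confounder | Plan's rule, correlation 0.1-0.3 | Plan's rule, correlation 0.4-0.5 | Forced | Fix |
|---|---|---|---|---|
| Linear, coefficient 0.10-0.25 | 5.1-7.4% | 7.2-13.0% | 4.5-5.2% | 4.8-5.6% |
| Logistic, prevalence 10-50%, odds ratio 1.25-1.75 per SD | 4.5-7.2% | 5.6-12.2% | 4.3-5.1% | 4.5-5.6% |

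**Linear model with a true effect of 0.4.** Mean bias under the plan's rule is 0.003-0.019 at correlations of 0.1-0.3 and 0.013-0.034 at 0.4-0.5. At 0.4-0.5 the confounder passes the 10% criterion in 46-93% of runs, and the p < 0.05 step then removes it in 15-73% of those.

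**Stronger confounders.** With no true effect and correlation 0.4-0.5, the retention step removes a confounder that met the 10% criterion as follows:

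| Confounder coefficient | Removed after passing 10% | False positives |
|---|---|---|
| 0.25 | 35-40% | 9.0-12.8% |
| 0.4 | 3-5% | 5.9-6.8% |
| 0.5 | 0.1-0.3% | about 5% |

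**The case against.** The best counter-argument concerns weight, not text. The harm needs a confounder that is well correlated with the exposure and has only a modest effect on the outcome, roughly 0.1-0.3 in standardised terms. A strong confounder is significant and stays in. At the planning effect of 0.4 the bias is at most about 0.034, or 0.034/0.4 = 8.5% of the effect, and detection stays within 1.7 percentage points of forced adjustment. No variable in the protocol is shown to lie in the harmful window. Some obvious candidates are partly handled already: blood pressure is standardised for age, sex and height, and hypertrophy is defined by percentile for age and sex. All of this stands. It limits the size of the problem but does not remove the conflict: obesity, renal function and medication, all collected under Data Collection, must still pass through the rule.

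The remedy is also imperfect. A change above 10% does not prove confounding. In logistic models it can reflect non-collapsibility, and when the crude coefficient is near zero a trivial shift can exceed 10%. Harm and precision cost were simulated separately, so the net gain in a realistic mixture of confounders and noise has not been shown. That also stands, and it is why the cost is set out with the fix.

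Finally, the analysis plan, which is not shown, might qualify the rule. But the protocol states the rule outright, so this is not detail left for later.

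**Conclusion.** The point holds and should be fixed. As written, the retention sentence can undo the confounding control that criterion (ii) is meant to provide, and criterion (i) does not say what it must mean.

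The size depends on assumed confounder strengths. With one modest confounder and no true effect, the error rate is little affected at correlations up to about 0.3. At 0.4-0.5 it reaches 7.2-13.0% in linear models and 5.6-12.2% in logistic models. A correlation of about 0.4 is necessary for material harm but not sufficient, because the harm largely disappears once the confounder's own coefficient reaches about 0.4. Harm with several confounders, or with sex and race also in the model, was not simulated. Confidence is high that the rule conflicts with itself. How much it would matter in this study's data cannot be known from the protocol. No sample-size or power figure changes.

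**What to change.** 1. Delete the p < 0.05 retention sentence, or limit it so that it cannot remove sex, race or any covariate that meets the 10% criterion.
2. State that sex and race stay in every model whatever their p-value.
3. Reword criterion (i) so that the candidate must be associated with both the predictor and the outcome at p < 0.2.

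This is wording only and needs no new data. The cost is precision, because some non-confounders will pass the 10% test and stay. A pure-noise candidate passes in about 38-40% of runs when there is no true effect. With a true effect it passes far less often: 1.0% in the linear model at 0.4, and in the logistic model at the protocol's odds ratio of 1.15 (SD 8.4), 6.8% at 15% prevalence and 1.8% at 50%.

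The cost falls mainly on hypertrophy at 12 months, since the Sample Size and Power section says "we estimate the prevalence of left ventricular hypertrophy is 40-60% before and 10-20% after treatment". That is 10-20 events in 100 subjects. The ratio, sex and a three-group race variable use 4 parameters, giving 10/4 = 2.5 to 20/4 = 5 events per parameter before anything is added. With six noise candidates and no true effect:

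- 2.3-2.4 stay on average, leaving 10/6.42 = 1.6 to 20/6.37 = 3.1 events per parameter;
- the spread of the estimate rises by 10-15%;
- false positives are 5.5-5.9%, against 4.2-4.9% unadjusted.

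With three candidates, 1.1-1.2 stay and the spread rises by 4-6%. A short candidate list therefore keeps the cost low, although some error inflation from data-driven entry remains.
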